Across the sites 60 patients will be enrolled to achieve 40 FEAST patients who will fully complete this study at the MUSC Institute of Psychiatry, Brain Stimulation Service (BSS) in Charleston, SC, and at GRU in Augusta, GA and Aiken, SC. At both MUSC and GRU, roughly matched 30 patients (each) will also be recruited from those scheduled to receive UB RUL ECT to obtain a cohort of 40 RUL comparison patients. The FEAST and UB RUL ECT groups must meet identical inclusion/exclusion criteria and will undergo identical evaluation procedures. The only difference between the groups will be that one receives FEAST and other UB RUL ECT. The treatment received by the UB RUL ECT group will not be affected by participating in this protocol. This is an open label, non-randomized, non-masked study. Separate consent forms will be used in each group. We are thus asking FDA permission to study 60 patients with FEAST. An additional 60 patients will be studied who receive conventional ECT. Even though they are getting conventional ECT, they are covered by this FDA IDE as their data will be used for comparison purposes with FEAST.

Patients will be selected from those referred for ECT for the treatment of major depressive episode. To verify diagnosis, the SCID-P will be administered to derive DSM-V diagnosis (unipolar or bipolar major depressive episode) and relevant subtypes and specifiers (American Psychiatric Association, 2013).

Inclusion and exclusion criteria are presented in Table 2. Briefly, patients will be between the ages of 18 and 90 years and will provide informed consent. Exclusions include: history of schizophrenia, schizoaffective disorder or any non-mood disorder psychosis, rapid cycling bipolar disorder, central nervous system illness other than conditions associated with psychotropic exposure, alcohol or substance abuse or dependence in the past 3 months, pregnancy, epilepsy, inability to have stable medications, and ECT within the past six months.

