Medication Status. Patients will be stabilized on their medications for 7 days and will be withdrawn from lithium and anticonvulsants for at least 5 days. ECT starts after completion of the baseline battery, usually after an additional 1-2 days. PRN lorazepam is limited to 3 mg/d, and is withheld approximately 10 hr before a treatment. A daily log is kept of all medications (psychotropic or otherwise) patients receive. Introduction of any medication during the FEAST (or UB RUL ECT) will be considered a protocol violation but will not lead to termination from the study.

General Treatment Technique. After completion of the pretreatment assessment battery, treatment with FEAST will begin. FEAST will be administered only with the modified Spectrum 5000Q device approved with this IDE application. Treatments are given in the morning, 3 times per week. Pharmacological agents are standardized: atropine (0.4 mg IV), methohexitol (0.75 mg/kg) and succinylcholine (0.75-1.0 mg/kg). [If methohexitol is unavailable, thiopental is substituted (2.0 mg/kg).] Patients are oxygenated by mask (100% O₂) prior to anesthesia and until resumption of

spontaneous respiration. Standardized procedures are used to reduce impedance at FEAST and EEG electrode sites. The impedance of the EEG electrodes is kept ~ 5k ohms.

The "cuff technique" assists in monitoring the duration of ictal motor activity (Fink and Johnson, 1982). The EEG sites are left and right frontal (F7 and F8) and a custom placement for the left and right temporal leads (to avoid overlap with the RUL ECT electrodes). Each EEG site is referenced to the ipsilateral mastoid (Weiner and Krystal, 1993). A detailed manual is available that describes detailed procedures for preparing the FEAST or RUL ECT electrode sites and the EEG sites. As indicated the primary hypothesis tested in this study concerns the ictal EEG collected at every treatment. We predict that seizure onset will be more restricted to the right frontal site with FEAST compared to UB RUL ECT.

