Table 5: Schedule of Procedures/Assessments

Assessment or Measurement	Screening Visit (s)	MRI Visit	ECT Weekly Assessments	End Of Acute Study	MRI Visit #2	2 month, 4 month, 6 month follow-up
---------------------------	---------------------	-----------	------------------------	--------------------	--------------	-------------------------------------

Informed Consent	X					
Study Information	X					
Demographics	X					
Medical Workup	X					
SCID and other treatment assessment battery (table 3)	X			X No SCID		
HRSD 24	X		X	X		X
ATHF/medications	X			X		X
Cognitive Battery	X			X		X
MRI scan		X			X	

B.13 Neurophysiology

Four-Channel Ictal EEG. At each treatment, 4 channels of EEG are recorded with the MECTA Spectrum amplifiers (1.4-48 Hz bandpass, -3dB, 12 dB/octave), and digitized and archived with MECTA EMR software. The spatial positioning of the frontal and temporal EEG electrodes, the preparation of each electrode site, and the referencing to ipsilateral linked mastoid EEG electrodes are detailed in a study manual. At each session, impedance of the each referenced pair is determined to be below 5k ohms.

The 4-channel EEG recordings are manually artifactual to remove non-encephalopathic signals. Expert visual inspection is used to define for each session the temporal periods characterized as preictal baseline (20 seconds prior to stimulus delivery), tonic phase (post-stimulus to onset of prominent low wave activity), clonic phase (end of tonic until offset of seizure activity in all channels) and postictal period (20 s following the termination of the seizure). These 4-channel ictal recordings are analyzed in a fashion identical to the procedures we have previously employed, but with the addition of measures of coherence (Luber et al., 2000, Nobler et al., 2000a). Power spectral analyses will be conducted, using a moving Hanning window and apply a Fast Fourier Transform to yield power and coherence data for each electrode site and measurement period for delta, theta, alpha, and beta frequency bands. The 4-channel recordings allow averaging across treatments to enhance reliability of measurement, and examination of cumulative effects (Krystal et al., 1998, Krystal et al., 1996a, Krystal et al., 1997, McCall et al., 1996a).

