The primary aim of this study is to contrast FEAST and UB RUL ECT in these EEG measures of seizure onset and propagation. Specifically, we expect FEAST to show greater focality of seizure onset than UB RUL ECT, with seizure onset most manifest in the right frontal EEG with FEAST, and far greater activity in the left and right temporal leads with UB RUL ECT.

B.14 Quality Assurance and Data Management

A highly experienced rater will provide clinical ratings throughout the treatment period. Accuracy of the output of the FEAST device will be tested ([name] et al., 1994), and calibration signals regularly applied to the EEG recordings. The stimulus parameters used with the modified Spectrum 5000Q will both be recorded electronically and transferred to a database using the Spectrum's automatic EMR logging software. An experienced psychometrician will review all neurocognitive data. Data will be entered on digital forms using automatic flags for out-of-range and missing values. Any correction to a data record will be recorded in an audit notebook. The study database will be backed-up regularly.

B.15 Statistical Analyses

Data Screening. Data will be reviewed for extreme values. When distributional assumptions are not met, data will be transformed or nonparametric procedures used. Prior to statistical analyses, the study sites (MUSC vs. GRU) and treatment groups (FEAST vs. UB RUL ECT) will be compared in the baseline sociodemographic and clinical features, using ANOVA and log-linear analyses, with a liberal threshold to detect inequality ($P < 0.2$).

Hypothesis Testing. Even though this is a preliminary investigation, yielding effect sizes by which to power a subsequent randomized study, it is important to protect the Type I error rate by limiting primary analyses to a restricted and clearly specified set of hypotheses and outcome measures. The primary analyses will test the hypotheses stated below which address the objectives described in Section II. The major areas of investigation are effects on seizure threshold, electrophysiological (EEG) activity, efficacy, function, objective changes in cognition and subjective cognitive changes. The primary efficacy analyses will be conducted in the intent-to-treat sample.

Hypothesis 1. FEAST is substantially more efficient (i.e., lower ST) than traditional ECT, even when both use an ultrabrief (0.3 ms) pulse width.

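### The primary EEG measures rest on manual artifact removal and visual phase marking, and the plan makes no provision for masking the readers to treatment group

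*Combined protocol and SAP*

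**What the plan says.** All references are to the combined protocol and SAP.

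- **Role of the EEG.** B.13 states: "The primary aim of this study is to contrast FEAST and UB RUL ECT in these EEG measures of seizure onset and propagation". B.6 agrees: "As indicated the primary hypothesis tested in this study concerns the ictal EEG collected at every treatment". B.5 places efficacy and side-effect comparisons second to it.
- **Artifact removal (B.13).** "The 4-channel EEG recordings are manually artifactual to remove non-encephalopathic signals" (evidently meaning that artifacts are removed by hand). No rejection rule is given.
- **Phase marking (B.13).** "Expert visual inspection is used to define for each session the temporal periods characterized as preictal baseline". The baseline is a set 20 s before the stimulus. The tonic epoch starts once the stimulus is over and closes when slow waves are judged to have become conspicuous. The clonic epoch follows and closes when the reader judges that no lead shows seizure activity any longer. The last epoch is given as "postictal period (20 s following the termination of the seizure"), so its length is set but its start depends on that same judgement.
- **Use of the epochs (B.15, Hypothesis 2).** Spectral power is computed after artifact removal, the epochs are averaged separately, and the log10 values enter MANCOVAs with site and treatment group as factors and age as covariate.
- **Masking.** B.1 states: "This is an open label, non-randomized, non-masked study". B.6 has the four EEG channels entered into the database together with the treatment parameters. B.14 covers EEG calibration signals but not reader masking, reader agreement or a second reader.
- **Expected direction.** B.13 and Hypothesis 2 both predict that FEAST seizures will be more focal, with the greatest expression at the right frontal lead.

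**The concern.** The Fourier analysis is objective, but a person chooses its inputs: which segments are discarded and where a seizure phase begins and ends. If that person knows the group and expects a particular result, small consistent choices can push the group difference in the predicted direction. Averaging over a patient's treatments reduces random error but leaves a consistent error in place. Adjusting for site and age does not remove an error that follows treatment group.

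At stake are the primary contrast and what follows from it. B.15 says the study is to yield effect sizes for powering a randomized trial, so an inflated difference would carry over into that trial's sample size. Open-label treatment does not force open-label reading: the recordings are digitized and archived, so they can be read later without the group label.

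**Working it through.** The plan gives no sample-size calculation, alpha, SD or effect size for the EEG comparison, so there is no figure to reproduce. The check has two parts: where reader judgement enters each sub-hypothesis, and what a given amount of bias would do.

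**1. Where judgement enters**

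- *Preictal baseline:* a fixed 20 s before the stimulus. Boundary marking does not affect it.
- *Tonic/clonic boundary:* judged. Moving it transfers seconds between two ictal epochs that are averaged separately.
- *Seizure end:* judged, once for all channels. It closes the clonic epoch and starts the 20 s postictal window.
- *Artifact removal:* judged, and nothing says it must be applied alike to all leads.

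**2. Shared boundaries and the lead contrasts (2c to 2e)**

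Suppose right-side power is k times left-side power throughout the recording. Then for any window common to both leads

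(r − l)/(r + l) = (k − 1)/(k + 1).

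With k = 1.5 this is 0.5/2.5 = 0.20 wherever the window is placed. The same holds for the frontal/temporal ratio. A boundary shift shared by all leads therefore does not create asymmetry, unless the ratio between leads changes over time.

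**3. Seizure end and postictal power (2b)**

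If the end is marked s seconds early, and ictal power is R times postictal power, mean power in the 20 s window is multiplied by

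((20 − s) + s·R)/20.

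With s = 1 (assumed) and R = 3, 10 or 30 (assumed range):

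- (19 + 3)/20 = 1.10
- (19 + 10)/20 = 1.45
- (19 + 30)/20 = 2.45

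These are rises of 10%, 45% and 145%. Higher postictal power means less suppression, which 2b predicts for FEAST. For ictal power (2a) the direction depends on how power changes through the seizure, which the documents do not give. One shift need not favour both hypotheses.

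**4. Artifact rejection confined to one side (2c to 2e)**

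Assume equal true power on both sides, lognormal segment power with a log10 SD of 0.3 (natural-log SD σ = 0.691), and rejection of the top fraction q of left-side segments only. The ratio of left to right means is

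l/r = Φ(z(1−q) − σ)/(1 − q).

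| q | l/r | index (1 − l/r)/(1 + l/r) |
|---|---|---|
| 5% | 0.874 | 0.07 |
| 10% | 0.803 | 0.11 |
| 20% | 0.700 | 0.18 |

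The true index is 0 in each row.

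**5. Effect on the false-positive rate**

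Take 40 per group (B.1), a two-sided alpha of 0.05 (assumed) and no true effect. A reader bias of b SD in the patient-level measure gives a rejection rate, by normal approximation, of

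Φ(b/√(2/40) − 1.96) + Φ(−b/√(2/40) − 1.96), with √(2/40) = 0.2236.

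| b (SD) | rejection rate |
|---|---|
| 0 | 5% |
| 0.1 | 7.3% |
| 0.2 | 14.5% |
| 0.3 | 26.9% |
| 0.5 | 60.9% |

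For scale, 80% power needs a true difference of (1.96 + 0.84) × 0.2236 ≈ 0.63 SD.

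Parts 3 to 5 show sensitivity only. None of s, R, q, the 0.3 or b comes from the documents.

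**The case against.** Several points on the other side are sound.

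- **A reader might infer that the EEG readers are known to be unmasked.** No sentence says so, or says who they are. It follows only from the blanket statement in B.1 and the absence of any masking step. B.13 says the analysis repeats earlier published procedures, which cannot be checked from these documents. What stands is that the plan makes no provision for masking. If the readers are masked in practice, a sentence in B.13 would settle that part of the point.
- **A reader might infer that reader choices determine every Hypothesis 2 result.** They do not. Power is computed rather than scored, the baseline is fixed, and shared boundaries leave the lead contrasts largely untouched. Those contrasts carry the focality aim, and their main exposure is artifact rejection that differs by lead.
- **A reader might infer that bias of a known size will occur.** The documents support a possible route only. The number of recordings, or of seconds reassigned from one phase to another, does not measure bias in a planned test.
- **Masking may fail.** Residual stimulus artifact, or the marked asymmetry predicted for FEAST, could reveal the group. Masking alone also leaves the judgement without rules, so rules set in advance are needed as well.
- **The study is preliminary and openly non-masked,** with a masked randomized trial planned to follow. That limits the consequence, but it is no reason to leave a cheaply closed gap in the primary measure.

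**Conclusion.** The concern holds as a gap in the plan. Followed as written, it lets readers who may know the treatment group remove artifact and mark seizure phases for the primary comparison, with the expected direction already stated. Judged seizure end and the tonic/clonic boundary mainly expose 2a and 2b; lead-specific artifact rejection is the main exposure for 2c to 2e.

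The size is unknown. Under the stated assumptions, a bias of 0.1 to 0.3 SD would raise a nominal 5% error rate to about 7% to 27%. The documents do not show that the readers are unmasked in fact, or that any bias will arise. The conclusion rests on the absence of a masking provision, which is clear from B.1, B.6, B.13, B.14 and B.15 together. It should be corrected before any recordings are read.

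**What to change.** Add to B.13:

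1. Archived EEG files are exported under random codes, with patient, group, site, date, dose and device mode removed and the stimulus segment cropped.
2. Rules for artifact rejection and for seizure end are fixed in writing beforehand and applied alike to all leads.
3. The existing readers remove artifact and mark phases in all records, in random order, and the markings are locked before the codes are broken.

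This concerns offline reading for analysis only. Bedside EEG reading during treatment is unaffected, and no patient procedure is added.

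**Cost.** A coding and cropping step for several hundred recordings. As a rough workload, 80 patients × 8.8 sessions (the mean in the FEAST pilot, III.D.6) is about 704; the pilot covered FEAST only and had different stopping rules. Masking may be imperfect for the reasons given above.

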The protocol presented in this new IDE will be performed at two clinical sites (MUSC and GRU). At each site 20 patients will be recruited to receive treatment with FEAST, or a total of 40 FEAST patients across the sites. A contemporaneous group of 20 patients will be identified at each site who are receiving standard clinical treatment with UB RUL ECT. These patients will be matched to the FEAST sample (within site)

in the distribution of gender and diagnosis (unipolar vs. bipolar), and the mean, variance and shape of the distributions of age and baseline modified mini-Mental State score (mMMS) (Stern et al., 1987). This RUL cohort is also included under this IDE. [We considered but ultimately abandoned having a formal, blind randomization of patients to FEAST or RUL. While we ultimately hope to perform such a study, the data with FEAST are quite limited at present. There thus may not be true clinical equipoise. Similarly, although the FEAST side effects appear benign, there have still been less than 50 patients total ever treated with FEAST. We thus have settled on a non-randomized but loosely matched comparison group. This group is important for the analysis of the EEG and MRI data, and can also be used for rough comparison of efficacy and cognitive side effects. It is our hope that following this trial, there might be sufficient evidence of efficacy to enable a formal randomized definitive trial.

We will be applying to the NIH for funding to support the conduct of this protocol. This IDE will serve to gather important pilot data and will serve as the IDE for the NIH study, if it is funded.

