Only 6 parameter combinations will be used at initial titration, with a range of charge from 9.6 to 307.2 mC. If a patient does not have an adequate seizure at the highest of these settings (307.2mC) they will exit the protocol and be offered conventional ECT. [This has not occurred in any of the patients who have received FEAST.] The highest dosage that can be used in this study is 576 mC, the same as the maximal output of a standard domestic Spectrum 5000Q (576 mC).

The stimulating electrodes consist of a small (1.25") round stainless steel electrode and a larger poster stainless steel electrode (2 x 3") that attaches in a standard manner to the MECTA remote-treat or standard stimulus cables. This smaller electrode will be placed anteriorly with the lower boundary just above the center of the right eyebrow. The larger posterior electrode is concave in shape to better couple to the scalp. The posterior electrode will be placed tangential to the midline and extend across the right supplementary motor cortex. The medial position of this electrode will be adjacent to the line connecting the nasion and inion and with the posterior boundary 1.0" anterior to the vertex, with the lateral portion extending over the right hemisphere. A self-adhesive locator will be used to position the anterior anode electrode, ensuring restriction of any conductant gel to the geometry of the anode.

Unless otherwise contraindicated, all patients will be premedicated with atropine (0.4 mg IV) to block the parasympathetic effects of electrical stimulation (approximately 2 minutes prior to anesthetic induction). As indicated, methohexitol (1.0 mg/kg) will be used as the general anesthetic and succinylcholine (0.75 mg/kg) will serve as the muscle relaxant. Dosing of these agents after the first treatment will be based on anesthetic response. Patients will be oxygenated from prior to the induction of anesthesia until the return of spontaneous respiration.

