The four-lead EEG digitized at each treatment will be subjected to a FFT after artifacting, and power computed in 4 frequency bands, as well as total power across bands. The baseline, tonic, clonic and postictal epochs will be averaged separately. After testing for multivariate normality, MANCOVAs will be applied to the ictal and postictal power (\log_{10}) values, using Site and Treatment Group as between-subject factors, and age as a covariate. Hypotheses 2a and 2b call for opposite main effects in the ictal and postictal analyses. Hypotheses 2c and 2e predict an interaction between Treatment Group and the laterality repeated measures factor. Thus, an asymmetry index $[(r-l)/(r+l)]$ will be greater with FEAST than conventional stimulation. Similarly, Hypotheses 2d and 2e calls for an interaction between Treatment Group and frontal vs. temporal lead placement. Finally, Hypothesis 2f states that measures of ictal and postictal power have at most weak relations with efficacy. Percent change

in HRSD₂₄ scores will be added to the MANCOVAs as a covariate. Main effects of clinical improvement and first and second-order interactions will be modeled.

Hypothesis 3. In contrasting resting fMRI data, both FEAST and UB RUL ECT result in a reduction of (heightened) frontal connectivity, replicating previous findings (Abbott et al., 2013, Beall et al., 2012, Perrin et al., 2012). However, this effect is especially focal within the FEAST group, and more restricted to right frontal regions.

MANCOVAs will be conducted with Site and Treatment Group as between-subject factors, age as a covariate, and time (pre-post) and connectivity values in a priori brain regions as repeated measures factors.

Hypothesis 4. Efficacy as assessed immediately following the treatment course does not differ between the FEAST and UB RUL ECT groups.

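### Hypotheses 2a and 2b are tested on absolute ictal and postictal EEG power with no preictal term, although a preictal epoch is recorded at every session

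*Combined protocol and SAP*

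**What the plan says.** Section B.13 (Neurophysiology) has four EEG channels recorded at each treatment and split by expert inspection into epochs, beginning with "preictal baseline (20 seconds prior to stimulus delivery), tonic phase (post-stimulus to onset of prominent low wave activity" and followed by the clonic and postictal periods. It adds that "The 4-channel recordings allow averaging across treatments to enhance reliability of measurement", and that "These 4-channel ictal recordings are analyzed in a fashion identical to the procedures we have previously employed", citing two earlier papers.

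Section B.15, Hypothesis 2, states that "The baseline, tonic, clonic and postictal epochs will be averaged separately". The next step is that "MANCOVAs will be applied to the ictal and postictal power" (log10), with site and treatment group as between-subject factors and age as covariate. The tests of interest follow: "Hypotheses 2a and 2b call for opposite main effects in the ictal and postictal analyses". The only covariate added later is percent change in HRSD24, for 2f.

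Section B.1 describes the study as open label, non-randomised and non-masked, with 40 patients per group. The overview before section B says the comparison group is matched "in the distribution of gender and diagnosis (unipolar vs. bipolar), and the mean, variance and shape of the distributions of age" and baseline mMMS. No EEG variable is listed. The liberal baseline screen in B.15 (P < 0.2) covers sociodemographic and clinical features.

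**The concern.** A preictal reference is defined, recorded and averaged, and then drops out of the stated model. It is not a covariate, a ratio denominator or a level of a repeated-measures factor. Two consequences follow.

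- **2a and 2b, comparability.** Group membership is by choice and referral. If FEAST patients happened to have lower EEG power in every epoch, their lower ictal power would look like support for 2a, and their lower postictal power would count against 2b. Neither would be an effect of treatment.
- **2b, construct.** Suppression means a fall from some level. The model looks only at where postictal power ends up.

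Elsewhere the plan does adjust for the starting value of an outcome: baseline HRSD24 in Hypothesis 4 and baseline CUAMI-SF in Hypothesis 5. Section B.15 also says the study should yield effect sizes for powering a later randomised trial, so a distorted estimate could be carried forward.

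**Working it through.** The documents give no power, SD, alpha or effect size for Hypothesis 2, so there is no planned figure to reproduce.

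**Construct check for 2b.** Let B be preictal and P postictal power in a session. Suppression is log10 B − log10 P. Two patients with the same P and different B differ in suppression but have the same value in the stated model. This holds whatever the correlation between epochs.

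**Inputs for scale.** From the documents: 40 per group (B.1). Assumed: two-sided 0.05; 80% power; r, the correlation of error-free log10 preictal power with the outcome; reliability (rel) 0.5 for a single 20 s epoch; preictal imbalance δ, in SD units.

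**Detectable difference.** The standard error of a group difference, in SD units, is √(2/40) = 0.224. The normal approximation gives (1.960 + 0.842) × 0.224 = 0.626. Noncentral t with 80 − 5 = 75 df (intercept, site, group, site × group, age) gives 0.635. One added covariate leaves 74 df and a residual SD of √(1 − r² × rel).

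| r | residual SD, rel 0.5 | detectable, rel 0.5 | detectable, error-free |
|---|---|---|---|
| 0.2 | √(1 − 0.020) = 0.990 | 0.628 | 0.622 |
| 0.3 | √(1 − 0.045) = 0.977 | 0.620 | 0.605 |
| 0.5 | √(1 − 0.125) = 0.935 | 0.594 | 0.550 |
| 0.7 | √(1 − 0.245) = 0.869 | 0.552 | 0.453 |

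**Bias with no treatment effect, δ = 0.3 SD.** Unadjusted bias is r × δ. After adjustment for a covariate of reliability rel it is r × δ × (1 − rel), so half remains at rel 0.5.

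| r | unadjusted bias | type I error | adjusted bias | type I error |
|---|---|---|---|---|
| 0.1 | 0.030 | 5.2% | 0.015 | about 5% |
| 0.2 | 0.060 | 5.8% | 0.030 | about 5% |
| 0.3 | 0.090 | 6.8% | 0.045 | 5.5% |
| 0.5 | 0.150 | 10.2% | 0.075 | 6.4% |
| 0.7 | 0.210 | 15.3% | 0.105 | 8.3% |

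At an extreme δ of 0.5 SD and r of 0.3, 0.5 and 0.7, type I error is 10.2%, 19.7% and 33.9% unadjusted, and 6.3%, 8.9% and 14.1% adjusted.

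**Cost of adjusting for preictal power averaged over sessions.** Take 8.8 sessions (the pilot mean in section D.6). Spearman-Brown gives 8.8 × 0.5 / (1 + 7.8 × 0.5) = 0.90, so the average is far less noisy. But if treatment itself shifts later preictal power by 0.2 SD, with no imbalance, the contrast is displaced by r × 0.9 × 0.2 = 0.054, 0.090 and 0.126 SD at r = 0.3, 0.5 and 0.7. Type I error is then about 6%, 7% and 11%, where the unadjusted model would hold 5%.

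**Why 2c–2e largely escape.** The index (r − l)/(r + l) is unchanged if all power is multiplied by a constant, and frontal-versus-temporal differences in log power cancel a common shift. Only a preictal difference in topography would reach them.

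**The case against.** The strongest reply is that this argues from silence. B.13 says the recordings are analysed as in earlier work, which may include baseline normalisation. That is possible but cannot be checked from the documents, and B.15 writes out an explicit model without such a term. If baseline use was intended, one sentence settles it.

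Second, the comparison with HRSD24 and CUAMI-SF is imperfect. The preictal epoch is a different brain state from the seizure, and orientation time, also averaged over sessions, has no baseline covariate. This weakens the case for 2a. It does not touch 2b, where the outcome's name implies a reference.

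Third, there are safeguards. Section B.6 standardises agents and has lorazepam capped and withheld before treatment, B.7 treats the groups alike except as noted, and B.2 compares medication status. These reduce the risk, but none puts preictal EEG into the model. B.6 also says "Dosing of these agents after the first treatment will be based on anesthetic response", so conditions can drift after session 1, and a session 1 covariate does not capture that.

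Fourth, every magnitude is assumed. This stands in full.

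A reader might infer that the primary focality aim is compromised. The documents do not support that: focality rests on within-patient lead contrasts. A reader might also infer that a preictal imbalance exists, or that adjustment would remove it. No document shows an imbalance, and a single noisy epoch removes only part of any bias. Nor does this point require a single tonic-epoch contrast or a statement on masking of EEG readers. B.15 already names the laterality and frontal-versus-temporal interactions, and B.1 calls the study non-masked.

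**Conclusion.** The concern holds in a limited form. As written, 2a and 2b are group comparisons of absolute power in non-randomised groups, adjusted for site and age only, while a usable reference epoch is left idle. The case is clearest for 2b, where the stated analysis does not isolate suppression. For 2a it concerns modest confounding and lost precision.

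At an assumed reliability of 0.5, the detectable difference improves from 0.635 SD to between 0.620 and 0.552 SD for r of 0.3 to 0.7. At r of 0.2 or less the gain is negligible, and a 0.3 SD imbalance inflates type I error only to 5.2–5.8% at r of 0.1–0.2. The inputs r, reliability, imbalance, alpha and power are assumptions; only the group size comes from the documents. Confidence is medium. The change is worth making because it is nearly free, not because the trial's main aim depends on it.

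**What to change.** In B.15, Hypothesis 2:

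1. **Models for 2a and 2b.** Add as a covariate log10 total preictal power, averaged over the four leads, from the 20 s before the first stimulus of session 1. For band-specific results, use preictal power in the same band.
2. **Outcome for 2b.** Analyse postictal power relative to same-session preictal power, either as a log-ratio with log10 preictal power kept as a covariate, or as postictal power with same-session preictal power as a covariate. In a linear model with that covariate the two give the same group estimate. Exclude windows that follow a subconvulsive stimulus: restimulation comes 20 s later (B.6), so such a window is not a resting reference.
3. **Sensitivity analyses.** Report the present unadjusted model for both and, for 2a, the same-session-adjusted result. State that preictal power after session 1 may itself reflect treatment. That caution also applies to reading 2b, where it is the price of measuring suppression.

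If the earlier procedures cited in B.13 already do some of this, write it into B.15.

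Cost: SAP wording and some extra model runs. No new data are needed, since every epoch is already recorded and averaged. The downsides are a small gain if the correlation is low, incomplete bias removal from one epoch, and more than one result to read for each claim.
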